### 2.2.2. Clinical Hypothesis Supporting Utility of Ravulizumab in COVID-19

Clinical evidence suggests that complement is activated during SARS infection and that the progression of severe pneumonia, acute lung injury, or ARDS in these patients is strongly associated with complement activation. The C3c fragment is present in the sera of patients with SARS and is a strong indicator of disease severity (Pang, 2006). Consistent with this finding, the complement activation product C5a is associated with the inflammatory response and severe lung damage that occurs in patients infected with the 2009 H1N1 influenza virus (Ohta, 2011). It has also been shown that SARS-CoV can directly activate complement via the lectin pathway (Ip, 2005). Patients with SARS develop autoantibodies against human epithelial cells and endothelial cells that mediate complement-dependent cytotoxicity (Yang, 2005).

Multiple lines of evidence support the hypothesis that complement is a key mediator of virally-induced lung damage and that acute lung injury associated with CoV infection is partially mediated by complement (Wong, 2004). Therefore, it is plausible to hypothesize that COVID-19-related injuries and multiorgan failures are mediated, at least in part, by complement activation. The existing data point to the role of C3 and the terminal complement complex, but not the alternative pathway alone. Inhibition of complement, specifically at the terminal complement node through inhibition of C5, may control the inflammatory processes which drive ARDS.

At present, there are no therapies that have received global approval by regulatory authorities for the prevention and/or treatment of COVID-19. China's National Health Commission recently updated treatment guidelines for COVID-19 recommending the use of tocilizumab (anti-interleukin [IL] 6R monoclonal antibody [mAb]) to treat Chinese patients infected with SARS-CoV-2 who have developed serious lung damage and have elevated levels of IL-6 in the blood. A variety of supportive therapies are being used in an attempt to improve prognosis in critically ill patients with confirmed COVID-19 presenting with severe pneumonia, acute lung injury, or potentially life-threatening ARDS. Despite the use of these supportive agents, patients have continued to experience deterioration of respiratory function, a critical contributor to fatal outcomes.

Ravulizumab is a mAb that specifically binds to the complement protein C5 with high affinity, thereby inhibiting its cleavage to C5a and C5b (the initiating subunit of C5b-9) and preventing the generation of the terminal complement complex C5b-9. This mechanism of action provides a therapeutic rationale for the use of ravulizumab in diseases in which complement activation is involved. In addition, the selective blockade of complement cascade at C5 by ravulizumab preserves the activity of upstream components of the complement cascade that are known to be essential for opsonization of microorganisms and prevention of immune complex disorders (Prodinger, 1999). Importantly, C5 blockade preserves the immunoprotective and immunoregulatory functions of early complement components.

Complement inhibition has been shown to be an effective therapeutic target in hematological and neuroinflammatory diseases. Ravulizumab is proposed for the treatment of patients with confirmed SARS-CoV-2 infection with a clinical presentation consistent with COVID-19 severe

pneumonia, acute lung injury, or ARDS. Treatment with ravulizumab produces complete and sustained inhibition of C5-mediated terminal complement activity. Treatment with ravulizumab could improve outcomes in patients with COVID-19 severe pneumonia, acute lung injury, or ARDS.

## 2.3. Benefit/Risk Assessment

### 2.3.1. Risk Assessment

Potential risks associated with participation in this study and risk mitigation measures are enumerated in [Table 2](#).

**Table 2: Potential Risks and Mitigation Strategies**

Risks of Clinical Significance	Summary of Data/ Rationale for Risk	Mitigation Strategy
Identified risk		
Meningococcal infection	Patients who have not received a meningococcal vaccination within the past 5 years may be unable to receive meningococcal vaccinations prior to initiating treatment with ravulizumab during this study.	If vaccination cannot be confirmed, the patient should receive prophylactic antibiotics against meningococcal infection prior to initiating ravulizumab treatment and for at least 8 months from the final infusion of ravulizumab (only applicable to patients exposed to study drug).  When patients are vaccinated less than 2 weeks prior to treatment with ravulizumab or after initiation of ravulizumab, they should continue antibiotic prophylaxis for at least 2 weeks after meningococcal vaccination.
Potential risks		
Serious infections	Ravulizumab could increase the risk of infection in this patient population. This potential risk is based on the mode of action of ravulizumab and experience with the use of eculizumab. Since the relevance of serious infection with ravulizumab therapy has not been confirmed in clinical studies, this remains a potential risk.	Training healthcare professionals and patients about the potential risk of additional serious infection. Monitoring for signs and symptoms of serious infections will be conducted as part of routine safety assessments for this study. In addition to appropriate antibiotic coverage versus infection and opportunistic infections, guidelines for immune reconstitution and revaccination will be followed, as applicable.
Immunogenicity	Treatment with any therapeutic protein has the potential to induce an immune response. Potential clinical consequences may include severe hypersensitivity type reactions,	Across 350 patients enrolled in ravulizumab, Phase 3 clinical studies, 2 patients were reported with treatment-emergent ADAs.

Risks of Clinical Significance	Summary of Data/ Rationale for Risk	Mitigation Strategy
	decrease in efficacy and induction of autoimmunity, including antibodies to the endogenous form of the protein (Li, 2002; Casadevall, 2002).	Presence of anti-ALXN1210 antibodies will be assessed.
Infusion site or infusion-associated reactions	Protein therapies administered intravenously have the potential risk of causing local (infusion-site) reactions and systemic reactions (infusion-associated reactions).	Monitoring for infusion reactions will be conducted as part of routine safety assessments for this study. Management of potential infusion reactions is detailed in Section 10.6.
Pregnancy exposure/lactation	No studies of ravulizumab have been conducted in pregnant women. There are no data available on excretion of ravulizumab in breast milk.	Pregnant or nursing female patients will be excluded from participating in this clinical study. Patients and their spouses/partners must use a highly effective or acceptable method of contraception for a period of 8 months following the final infusion of ravulizumab. Breastfeeding should be discontinued during treatment and up to 8 months after the final infusion of ravulizumab.

Abbreviations: ADA = antidrug antibody.

### 2.3.2. Benefit Assessment

Potential benefits of study participation include:

- Improve survival rate of patients with SARS-CoV-2 infection who are receiving ravulizumab + best supportive care (BSC) compared with BSC alone
- Decrease lung injury in patients with SARS-CoV-2 infection while on supportive medical care
- Improve clinical outcomes in patients with SARS-CoV-2 infection while on supportive medical care

### 2.3.3. Overall Benefit: Risk Conclusion

Although the efficacy of ravulizumab has not been previously studied in patients with severe pneumonia, acute lung injury, or ARDS, the emerging evidence for the scientific rationale, the predicted drug concentrations and pharmacodynamic (PD) effects after administration of the recommended dose (Section 4.3), and its established safety profile indicate that ravulizumab is an appropriate candidate for clinical investigation, and that the potential for clinical benefit outweighs the risk of treatment with ravulizumab for patients participating in Study ALXN1210-COV-305.

The safety profile of ravulizumab is well characterized in the current clinical development programs, including approved indications in paroxysmal nocturnal hemoglobinuria (PNH) and

atypical hemolytic uremic syndrome (aHUS). Known and potential risks can be effectively managed with the risk mitigation strategies currently in place for ravulizumab.

More detailed information about the known and expected benefits and risks and reasonably expected adverse events (AEs) of ravulizumab may be found in the Investigator's Brochure (IB).

### 3. OBJECTIVES AND ENDPOINTS

**Table 3: Objectives and Endpoints**

Objective	Endpoints
Primary	
To evaluate the effect of ravulizumab + BSC compared with BSC alone on the survival of patients with COVID-19	
 
Survival (based on all-cause mortality) at Day 29
 

Secondary	
To evaluate the efficacy of ravulizumab + BSC compared with BSC alone on outcomes in patients with COVID-19	
 
Number of days free of mechanical ventilation at Day 29
 
Duration of intensive care unit stay at Day 29
 
Change from baseline in SOFA score at Day 29
 
Change from baseline in SpO2/FiO2 at Day 29
 
Duration of hospitalization at Day 29
 
Survival (based on all-cause mortality) at Day 60 and Day 90
 

Safety	
To characterize the overall safety of ravulizumab + BSC compared with BSC alone in patients with COVID-19	
 
Incidence of TEAEs and TESAEs
 

PK/PD/Immunogenicity	
To characterize the PK/PD and immunogenicity of ravulizumab in patients with COVID-19	
 
Change in serum ravulizumab concentrations over time
 
Change in serum free and total C5 concentrations over time
 
Incidence and titer of anti-ALXN1210 antibodies
 

Biomarkers	
To assess the effect of C5 inhibition on systemic activation of complement, inflammation, and prothrombic activity in patients with COVID-19	
 
Change in absolute levels of soluble biomarkers in blood associated with complement activation, inflammatory processes, and hypercoagulable states over time
 

Exploratory	
To evaluate the effect of ravulizumab + BSC compared with BSC alone on progression to renal failure requiring dialysis in patients with COVID-19	
 
Incidence of progression to renal failure requiring dialysis at Day 29
 

To evaluate the effect of ravulizumab + BSC compared with BSC alone on clinical improvement in patients with COVID-19	
 
Time to clinical improvement (based on a modified 6-point ordinal scale) over 29 days
 

To evaluate the effect of ravulizumab + BSC compared with BSC alone on the health-related quality of life of patients with COVID-19	
 
SF-12 PCS and MCS scores at Day 29 (or discharge), Day 60, and Day 90
 
EQ-5D-5L scores at Day 29 (or discharge), Day 60, and Day 90
 

Baseline is defined as the last available assessment on or before Day 1 for all patients. Day 1 will be defined as the date of the first infusion of ravulizumab for patients randomized and dosed with ravulizumab and as the date of randomization for patients randomized but not dosed with ravulizumab.

Abbreviations: BSC = best supportive care; C5 = complement component 5; COVID-19 = Coronavirus Disease 2019; EQ-5D-5L = EuroQol-5 Dimension-5 level; FiO2 = fraction of inspired oxygen; MCS = Mental Component Summary; PCS = Physical Component Summary; PD = pharmacodynamic; PK = pharmacokinetic; SF-12 = 12-item Short Form; SOFA = Sequential Organ Failure Assessment; SpO2 = peripheral capillary oxygen saturation; TEAE = treatment-emergent adverse event; TESAЕ = treatment-emergent serious adverse event.

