### 1.3. Schedule of Activities

**Table 1: Schedule of Activities**

Period	Screening Period	Primary Evaluation Period							Follow-up Period 	
		D1 	D5 	D10 	D15 	D22	D29/ Discharge 	Early Termination 	D60	D90
Study Day (D)	D -3 to D -1									
Study Window (days)	NA	NA	±1	±1	±1	±1	±1		±7	
Eligibility										
Informed consent	X									
Inclusion/exclusion	X									
Medical history 	X									
Demographics	X									
Study Administrative										
Confirmation of vaccination or appropriate antibiotic prophylaxis against N. meningitidis 	X								X	
Screening Laboratory Tests										
Confirmed positive SARS-CoV-2 test	X									
Chest CT or X-ray 	X									
Pregnancy test 	X						X	X		
Randomization										
Randomized to study drug + BSC or BSC alone		X								
Administration of Study Drug										
Ravulizumab 		X	X	X	X					
Efficacy Assessments										
Survival status										X
Mechanical ventilation status	X									
Hospitalization status										
Intensive care unit status										
Dialysis status										
FiO 2 , SpO 2 , PaO 2 										
Sequential Organ Failure Assessment score	X	X	X	X	X	X	X	X	X	
Safety Assessments										
Electrocardiogram	X						X	X		
Complete physical examination 	X						X	X		
Abbreviated physical examination 		X	X	X	X	X				
Glasgow Coma Scale	X	X	X	X	X	X	X	X		

Period	Screening Period	Primary Evaluation Period							Follow-up Period 	
		D1 	D5 	D10 	D15 	D22	D29/ Discharge 	Early Termination 	D60	D90
Study Day (D)	D -3 to D -1									
Study Window (days)	NA	NA	±1	±1	±1	±1	±1			±7
Body weight	X	X	X	X	X					
Vital sign measurements (predose) 	X	X	X	X	X	X	X	X		
Adverse event review and evaluation	X	<<monitor continuously>>								X
Review safety card 		X 					X 	X 		X 
Safety Laboratory Tests (Predose)										
Clinical chemistry	X	X	X	X	X	X	X	X		
Hematology	X	X	X	X	X	X	X	X		
Coagulation panel and D-dimer	X	X	X	X	X	X	X	X		
Urinalysis	X	X	X	X	X	X	X	X		
Direct Coombs test	X									

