PK/PD/Immunogenicity Tests										
PK 		X	X	X	X	X	X	X		
Total and free C5 		X	X	X	X	X	X	X		
Immunogenicity (predose) 		X					X	X		
Biomarker Tests										
Serum and plasma biomarkers (predose) 	X	X	X	X	X	X	X	X		
Other										
Concomitant medication 	X	<<monitor continuously>>								X
Nonpharmacologic treatments and therapies 	X	<<monitor continuously>>								X
Patient-reported Outcomes										
SF-12							X			X
EQ-5D-5L							X			X

. The Day 1 visit may occur on the same day as Screening.

. Patients randomized to ravulizumab + BSC will receive a weight-based dose of ravulizumab on Day 1 (Table 5). On Day 5 and Day 10, additional doses of 600 mg or 900 mg ravulizumab will be administered (according to weight category) and on Day 15 patients will receive 900 mg of ravulizumab.

. If a patient is discharged before the end of the Primary Evaluation Period (Day 29), the patient will undergo the early discharge assessments. In addition, the patient will be contacted via telephone on Day 29 to assess health status (eg, survival, mechanical ventilation, hospitalization, intensive care unit, and dialysis). Follow-up telephone calls should be performed as planned unless the patient withdraws consent.

. The Early Termination Visit is to be conducted when the patient discontinues from the study during the Primary Evaluation Period. In addition, the patient will be contacted via telephone on Day 29 to assess health status (eg, survival, mechanical ventilation, hospitalization, intensive care unit, and dialysis).

. Additional monitoring will be performed during the 2 follow-up visits to review patient status, including survival and pregnancy, and to obtain information about new or worsening TESAEs. The follow-up will be conducted as a telephone call if the patient is discharged from the hospital or an in-person visit if the patient is still hospitalized.

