#### **8.4.10. Hospital Discharge**

If a patient is discharged before the end of the Primary Evaluation Period, the patient will be contacted via telephone on Day 29 to assess health status (survival, mechanical ventilation, hospitalization, intensive care unit, and dialysis).

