#### **8.5.2. 12-item Short Form at Days 29, 60, and 90**

The Short-Form (SF)-12 is a validated health-related quality of life (HR-QoL) instrument that is widely used across a broad spectrum of disease indications. Adapted from the 36 -item SF survey that was designed to evaluate physical and mental health status, the SF-12 survey contains only 12 questions but covers the same 8 domains. There is a further stratification into 2 summary measures (Physical Component Summary [PCS-12] and Mental Component Summary [MCS-12]) as specified below.

- PCS-12

- General health (1 item)
- Physical functioning (2 items)
- Role physical (2 items)
- Body pain (1 item)
- MCS-12
  - Vitality (1 item)
  - Social Functioning (1 item)
  - Role Emotional (2 items)
  - Mental Health (2 items)

The PCS-12 and MCS-12 summary measures are scored using a norm-based method (ie, mean = 50, SD = 10) (Jenkinson, 1997). A PCS-12 or MCS-12 score of 50 indicates an average score with respect to a healthy population. Scores lower than 50 reflect less than average health and scores greater than 50 reflect better than average health (Ware, 1995).

The SF-12 assumes a recall of 1 week before responding to questions. The survey is anticipated to be completed in several minutes and can be completed by the patient or via an interviewer (in-person or over the telephone).

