### **8.5.3. EuroQol-5 Dimension-5 Level at Days 29, 60, and 90**

The EuroQol 5-dimension, 5 severity level (EQ-5D-5L) questionnaire is a brief, validated, HR-QoL instrument that is intended to assess the patient’s health status at the time of administration. The questionnaire contains 5 dimensions (mobility, self-care, usual activities, pain/discomfort, and anxiety/depression), each of which includes 5 response variables (no problems, slight problems, moderate problems, severe problems, and extreme problems) (EQ - 5D, 2019) There is no summary score generated upon completion, but rather a 5-digit profile (termed “health state”) based on each of the dimensions that can be further converted to a single numerical score (index value). Value sets (a collection of index values) have been derived for multiple countries/regions.

A vertical visual analogue scale (VAS) is included for patients to indicate a self-rated estimate of their health. The VAS ranges from 100 (best health you can imagine) to 0 (worst health you can imagine).

The EQ-5D-5L questionnaire and VAS are anticipated to be completed in several minutes and can be completed by the patient, via an interviewer (in-person or over the telephone); or via proxy.

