7.2.3.2. Time to Clinical Improvement over 29 Days

In addition, the time to clinical improvement will be evaluated, as defined by live discharge from the hospital, a decrease of 2 points from baseline on a 6-point ordinal scale, or both. Time to clinical improvement will be analyzed using the KM method and compared using a log-rank test stratified by intubated or not intubated on Day 1 as a sensitivity analysis. Hazard ratio and risk reduction will be summarized from a Cox proportional hazards model stratified by intubated or not intubated on Day 1. Confidence intervals (95%) will be presented for the clinical improvement estimate at Day 29 based on the complementary log-log transformation. Kaplan-Meier curves for both treatment groups will be produced.

7.2.3.3. SF-12 PCS and MCS Scores at Day 29 (or discharge), Day 60 and Day 90

SF-12 PCS and MCS scores at Day 29 (or discharge), Day 60 and Day 90 will be compared between treatment groups using an analysis of covariance (ANCOVA), adjusting for age and the randomization stratification factor.

7.2.3.4. EQ-5D-5L Scores at Day 29 (or discharge), Day 60 and Day 90

EQ-5D-5L index and VAS scores at Day 29 (or discharge), Day 60 and Day 90 will be compared between treatment groups using an analysis of covariance (ANCOVA), adjusting for age and the randomization stratification factor.

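### The Day 29 quality-of-life score is taken at discharge for patients who go home earlier, so this exploratory comparison mixes assessment times that depend on discharge

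*Protocol*

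**What the plan says.** Protocol Table 3 defines the two endpoints as "SF-12 PCS and MCS scores at Day 29 (or discharge), Day 60, and Day 90" and "EQ-5D-5L scores at Day 29 (or discharge), Day 60, and Day 90". The Synopsis and SAP 5.1.3 use the same timing.

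The Schedule of Activities (Protocol Table 1) places both questionnaires in a single column headed "D29/ Discharge", and again at the follow-up visits. Footnote 3 states: "If a patient is discharged before the end of the Primary Evaluation Period (Day 29), the patient will undergo the early discharge assessments". Protocol 8.4.10 adds that for such patients "the patient will be contacted via telephone on Day 29 to assess health status". It then lists survival, ventilation, hospitalization, ICU and dialysis; no questionnaire is named.

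On the instruments, Protocol 8.5.2 says "The SF-12 assumes a recall of 1 week before responding to questions", whereas 8.5.3 says EQ-5D-5L describes health when it is administered. Both allow telephone interview; EQ-5D-5L may be completed by the patient, "via an interviewer (in-person or over the telephone); or via proxy". The headings of 8.5.2 and 8.5.3 name Days 29, 60 and 90 and do not mention discharge.

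SAP 7.2.3.3 says "SF-12 PCS and MCS scores at Day 29 (or discharge), Day 60 and Day 90 will be compared between treatment groups" by ANCOVA with age and intubation stratum. SAP 7.2.3.4 does the same for the EQ-5D-5L index and VAS.

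**The concern.** A patient who leaves hospital on Day 10 and one who is still an inpatient on Day 29 contribute to the same time point, although they are measured 19 days apart. When the measurement is taken depends on an event after randomization. Protocol 9.1 hypothesises that ravulizumab reduces hospital days by Day 29. If it does, the arms are measured at different average times.

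For SF-12 the content shifts as well. A form completed at discharge looks back over mainly the last hospital week, in patients who all needed mechanical ventilation at entry, and says nothing about the time between discharge and Day 29.

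At stake is whether the first quality-of-life comparison can be read as a Day 29 result. Protocol 8.13 also allows these scores into economic analyses, where a discharge value read as Day 29 would carry over.

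**Working it through.** The plan states no sample size, effect or power for SF-12 or EQ-5D-5L, so there is no figure to reproduce. The check has two parts.

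**1. Which score is analysed for a patient discharged early?**

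- The endpoint wording allows discharge in place of Day 29.
- The schedule has one shared column, and footnote 3 sends the patient to the assessments at discharge.
- The Day 29 call lists five status items. Footnote 3 introduces them as examples; 8.4.10 gives the same five without that qualifier.
- After an early discharge, the next scheduled questionnaire is Day 60.
- SAP 9.4.6 defines analysis windows only for SpO2/FiO2 and PaO2/FiO2. Nothing separates a discharge score from a Day 29 score.

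The discharge score therefore stands in for Day 29. For a Day 10 discharge the gap is 29 − 10 = 19 days, and the SF-12 recall covers roughly Days 3 to 10. For a very short stay, part of the recalled week could precede admission.

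This concerns patients discharged alive before Day 29 who complete the forms. The Early Termination column carries no questionnaire.

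**2. How large could the effect be?** The documents give no discharge distribution and no recovery slope, so every input here is assumed:

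- control discharge day about Normal(22, SD 7), not below Day 3, with assessment capped at Day 29;
- ravulizumab discharge earlier by 0, 2, 4 or 7 days;
- scores rising by 1 to 4 points per week.

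*Scenario A: quality of life is identical in both arms on every calendar day.* The true Day 29 difference is 0.

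False difference = slope per week × (mean assessment day, ravulizumab − control) / 7.

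| Discharge earlier by | Mean assessment day, control / ravulizumab | At 1 point per week | At 4 points per week |
|---|---|---|---|
| 0 days | 21.4 / 21.4 | 0 | 0 |
| 2 days | 21.4 / 19.7 | −0.25 | −0.99 |
| 4 days | 21.4 / 17.9 | −0.51 | −2.03 |
| 7 days | 21.4 / 15.1 | −0.91 | −3.64 |

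The entries use unrounded means. From the rounded means, the 4-day row at 4 points per week is 4 × (17.9 − 21.4) / 7 = −2.0.

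*Scenario B: patients leave at the same state of health and recover at the same rate afterwards.* Take two patients, both home before Day 29, one discharged 4 days sooner. The true Day 29 difference is 1 × 4/7 = 0.57 to 4 × 4/7 = 2.29 points. Their discharge scores are equal, so the recorded difference is 0: a real difference is lost rather than reversed.

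Both scenarios assume that scores rise between discharge and Day 29. If they level off after discharge the shift disappears, and if they dip it changes sign.

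**The case against.** The strongest reply is that the timing is disclosed and has a purpose. Both documents state it openly, and a form completed at the bedside is less likely to be missed than one completed by telephone. The endpoints are exploratory, lie outside the closed testing procedure and carry no power claim. Day 60 and Day 90 are fixed for all patients (window ±7 days). All of this stands, and it limits the weight of the point. It does not make a discharge score on Day 10 and an inpatient score on Day 29 the same measurement.

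Three stronger readings are tempting.

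- *The comparison is turned against ravulizumab.* Scenario A gives that result, but Scenario B gives attenuation. The comparison group also includes patients still in hospital on Day 29, who may score lower. The documents contain nothing that decides between these.
- *The ANCOVA is wrong because it omits assessment day.* That day arises after randomization and may be affected by treatment. Adjusting for it could remove part of the effect or add bias, so leaving it out is not an error.
- *The hospital-week recall affects both instruments.* It applies to SF-12 only. The timing problem applies to both.

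**Conclusion.** The point holds for the first of the three quality-of-life time points. As planned, SF-12 and EQ-5D-5L at Day 29 compare arms on scores taken at discharge or on Day 29, with the day governed by an outcome the trial expects treatment to change. The comparison may be attenuated or biased.

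Its size cannot be read from the documents. Under the Scenario A assumptions it runs from 0, with no effect on discharge, to about −0.5 to −2.0 points for discharge 4 days earlier, against the SF-12 norm SD of 10. Those figures rest entirely on the assumed discharge days and recovery slope.

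A reader might infer that the quality-of-life objective cannot be answered. The documents do not support that: Table 3 states a general objective on health-related quality of life, and two of its three time points are unaffected. No confirmatory conclusion is touched.

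**What to change.** - For patients discharged before Day 29, administer SF-12 and EQ-5D-5L during the existing Day 29 telephone call and analyse those scores as Day 29. Add the questionnaires to the call in footnote 3 and Protocol 8.4.10.
- If the discharge form is kept, report it separately under the label *at discharge*.
- Delete the parenthetical *or discharge* from the endpoint in the Synopsis, Protocol Table 3 and SAP 5.1.3, 7.2.3.3 and 7.2.3.4, which then agree with the headings of Protocol 8.5.2 and 8.5.3.
- Do not add assessment day as a covariate.

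If the call cannot carry the questionnaires, name the endpoint as discharge or Day 29, whichever comes first, and report assessment day by arm. That makes the limitation visible but does not remove it.

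The cost is a few more minutes on a call already planned, edits to the schedule and SAP, and somewhat more missing Day 29 forms than at the bedside. Telephone follow-up of discharged patients is already planned at Days 60 and 90, when both questionnaires are due.
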